Bedside glucose safety measurements (SuperGL laboratory analyzer)		X		Samples will be collected throughout the study procedure. During the hypoglycemia induction procedure, plasma glucose concentration will be measured no more than 10 minutes apart while the plasma glucose concentration is ≥ 100 mg/dL and no more than 5 minutes apart when the plasma glucose concentration is < 100 mg/dL. Post-glucagon administration, plasma glucose concentration will be measured every 5 minutes for the first 30 minutes and every 10 minutes up to 90 minutes.
Sample collection for measurement of plasma glucose		X		Samples will be collected pre-dose (i.e., immediately prior to glucagon administration) and at 5, 10, 15, 20, 25, 30, 40, 50, 60, and 90 minutes post-glucagon administration. Samples to be processed at a central laboratory.
Exploratory sample		X (Period 1 only)	X	Serum samples will be collected prior to the procedure to induce hypoglycemia.

Genetic sample		X (Period 1 only)		
----------------	--	-------------------------	--	--

Abbreviations: CRU = clinical research unit; DPC = dodecylphosphocholine; ECG = electrocardiogram; ED = early discontinuation; HbA1c = hemoglobin A1c; IM = intra-muscular; NG = nasal glucagon; PG = plasma glucose.

Note: if multiple procedures take place at the same time point, the following order of the procedure should be used: ECG, vital signs and venipuncture.

3. Introduction

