7.2.1. Selection and Timing of Doses

The hypoglycemia induction procedure should be initiated at approximately the same time at each treatment visit. An IV infusion of insulin will be given until PG level of <60 mg/dL is reached. At this point, insulin infusion will be stopped and approximately 5 minutes later, a single-dose glucagon (NG or IMG) will be administered to the patients by CRU staff. The actual date and time of glucagon administration will be recorded in the patient's case report form (CRF).

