10.3.4. Pharmacodynamic Analyses

10.3.4.1. Pharmacodynamic Parameter Estimation

Pharmacodynamic parameters will be calculated using NCA. Key PD parameters will be derived to assess the exposure to glucose and duration of exposure above, below, and within the normal glucose range. The normal range for PG will be considered to be 70 to 108 mg/dL. Actual sampling times will be used for all calculations.

The following PD parameters will be calculated using concentrations of glucose:

$AUEC_{above}$	area under the effect concentration-time curve above the normal range
$AUEC_{below}$	area under the effect concentration-time curve below the normal range
$AUEC_{within}$	area under the effect concentration-time curve within the normal range
$AUEC_{0-1.5}$	area under the effect concentration-time curve from time zero (predose) up to 1.5 hours
BG_{max}	maximal blood glucose
$Duration_{above}$	duration above normal range
$Duration_{below}$	duration below normal range
$Duration_{within}$	duration within normal range
t_{above}	time to concentrations above normal range
t_{below}	time to concentrations below normal range (after t_{above})
t_{within}	time to concentrations within normal range
T_{max}	time to maximum concentration

The following PD parameters will be calculated using baseline-adjusted concentrations of PG:

$AUEC_{0-1.5}$	area under the effect concentration-time curve from time zero (predose) up to 1.5 hours
BG_{max}	maximal blood glucose
T_{max}	time to maximum concentration

Baseline PG concentrations will be calculated from samples obtained immediately prior to glucagon dosing (e.g., pre-dose).

Other PD parameters of PG may be calculated if required. Individual concentrations and PD parameters of PG will be summarized with descriptive statistics by treatment.

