10.3.4.2. Pharmacodynamic Statistical Inference

The PD parameters (such as BG_{max} and AUEC parameters) will be log-transformed prior to analysis and a linear mixed-effects model fitted to the data, with treatment, period, and sequence as fixed effects and patient as a random effect. For each parameter, the treatment difference will be back-transformed to present the ratios of geometric means and the corresponding 90% CI.

The values of T_{\max} will be analyzed nonparametrically using the Wilcoxon signed-rank test. Median differences and approximate 90% CIs for the difference will be calculated for the comparisons of treatments.

Exploratory analyses may be performed for other PD parameters as deemed appropriate.

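### The pharmacodynamic model for log BGmax and AUEC0-1.5 leaves out the visit's pre-dose glucose as a covariate and may give up a modest amount of precision

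*Protocol*

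**What the plan says.** Protocol Section 10.3.4.2 sets out the PD inference. The model terms are listed in full: "with treatment, period, and sequence as fixed effects and patient as a random effect". BGmax and the AUEC parameters are among the outcomes, and these "will be log-transformed prior to analysis and a linear mixed-effects model fitted to the data". On reporting, the section says that "the treatment difference will be back-transformed to present the ratios of geometric means and the corresponding 90% CI". Unlike Sections 10.3.1.2.1, 10.3.1.2.2, 10.3.2.2 and 10.3.2.3, this section does not leave further detail to the SAP, so the list of terms is a stated choice.

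Section 10.3.4.1 derives BGmax and AUEC0-1.5 twice. The first list opens "The following PD parameters will be calculated using concentrations of glucose", the second "The following PD parameters will be calculated using baseline-adjusted concentrations of PG". On the baseline itself it says: "Baseline PG concentrations will be calculated from samples obtained immediately prior to glucagon dosing". It does not say how the adjustment is made, or which set carries the main estimate.

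The Schedule of Activities (Section 2) provides a pre-dose PG sample in Periods 1 and 2, followed by a series of post-dose samples up to an hour and a half. On the timing of the pre-dose sample, Section 7.2.1 says that once PG is below 60 mg/dL the "insulin infusion will be stopped and approximately 5 minutes later, a single-dose glucagon (NG or IMG) will be administered".

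**The concern.** Each patient is brought to hypoglycaemia twice, and the starting glucose will not be identical. The infusion stops at any reading below 60 mg/dL, bedside readings may be up to 5 minutes apart below 100 mg/dL (Section 2), PG is still falling (Section 5.1), and the interval to dosing is approximate. If starting glucose carries over into the maximum or the area, the difference between a patient's two visits becomes residual noise in the planned model. A covariate measured before that visit's treatment could remove part of it.

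BGmax is a named secondary endpoint (Section 4). The primary outcome is close to its ceiling: 98% success is assumed for both products (Section 10.1), and the earlier Phase 3 study saw 74 of 75 and 75 of 75 (Section 3.2). The continuous PD comparison is therefore where a product difference would most readily show. What is at stake is the width of a 90% interval on a secondary, descriptive comparison, using data already collected.

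**Working it through.** The protocol gives no SD, correlation, interval width or power for any PD endpoint, so there is no figure of its own to reproduce. The 66 patients are sized on the binary primary outcome only.

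**Inputs**
- N = 66 patients completing both visits (Section 10.1).
- r: correlation between within-patient, visit-to-visit differences in baseline and in the log outcome. Not given; assumed over a range.
- k: SD of the baseline differences divided by SD of the outcome differences. Not given; assumed.

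**Covariate against the planned model.** With complete pairs, the treatment effect in a 2×2 crossover is estimated from within-patient differences. One covariate on those differences changes the variance by the factor

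(1 − r²) × (1 + 1/(N − 4)) = (1 − r²) × (1 + 1/62) = (1 − r²) × 1.0161.

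The second factor is the cost of estimating the slope. Interval width changes by the square root.

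| r (assumed) | Variance ratio | CI width |
|---|---|---|
| 0 | 1.016 | 0.8% wider |
| 0.1 | 1.006 | 0.3% wider |
| 0.126 | 1.000 | unchanged |
| 0.2 | 0.975 | 1.2% narrower |
| 0.3 | 0.925 | 3.8% narrower |
| 0.5 | 0.762 | 12.7% narrower |

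Break-even: 1 − r² = 62/63, so r = √(1/63) = 0.126.

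**Which r is plausible.** Assume a mean baseline of 47 mg/dL, a mean rise of 120 mg/dL that does not depend on baseline, a visit-to-visit baseline SD of 3 to 8 mg/dL, and a within-visit CV of the rise of 15% to 25% (SD 18 to 30 mg/dL). Approximately, r = SD(baseline)/√(SD(baseline)² + SD(rise)²).
- Lowest: 3/√(9 + 900) = 0.10, CI 0.3% wider.
- Highest: 8/√(64 + 324) = 0.41, variance ratio (1 − 0.165) × 1.0161 = 0.85, CI about 8% narrower.

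Simulation of the log-scale crossover under these settings gave variance ratios of 0.84 to 1.00, in line with this. All these settings are assumptions.

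**Do the baseline-adjusted parameters already do this?** Suppose the adjustment is a subtraction. On an additive scale its variance relative to ignoring baseline is 1 + k² − 2rk. At k = 0.5 and r = 0 this is 1.25, worse than ignoring baseline. At k = r = 0.5 it is 0.75, slightly better than the covariate's 0.762. So on that scale subtraction can recover the whole gain when the rise is independent of baseline.

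Section 10.3.4.2, however, takes logs. The log of a subtracted BGmax compares rises, so its back-transformed effect is a ratio of rises, whereas raw BGmax gives a ratio of maxima. In the simulation with baseline SD 3 mg/dL and CV 15%, the SD of the estimate was 0.0261 for the log ratio of rises and 0.0190 for the log ratio of maxima. These belong to different quantities, and neither can be read as the precision of the other. No planned analysis gives a covariate-adjusted ratio of maxima.

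**The case against.** The strongest reply is that nothing is wrong. Treatment order is randomised, the model is a standard crossover model that matches the PK model in Section 10.3.3.2, and omitting a baseline covariate neither biases the comparison nor invalidates the 90% interval. The PD objective is to characterise profiles, with no margin or power target. Section 10.3 lets the SAP change methods that are not principal features, and a reader will already see raw and baseline-adjusted results. The validity argument stands in full, as does the limited importance. The last argument stands only in part, because the two planned sets answer different questions once logs are taken.

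A reader might infer more than the protocol supports:
- **That precision is certainly lost.** It is not if r is below about 0.13, and induction keeps pre-dose PG fairly tight. The further fall of 15 to 20 mg/dL in Section 5.1 runs to the lowest concentration, which may come after dosing, since Section 10.3.1.1 looks for the nadir up to 10 minutes post-dose. It is not all spread in the pre-dose sample.
- **That the plan subtracts baseline, and so adds variance when the true slope is below 0.5.** Subtraction is the usual reading but is not stated, and the 0.5 rule (1 + k² − 2rk exceeds 1 when r/k is below 0.5) holds on an additive scale, not for the planned log analysis.
- **That one product is dosed systematically later, which would unbalance baseline.** Both follow the same rule of approximately 5 minutes (Section 9.2.2). Nothing in the protocol shows a difference.

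**Conclusion.** The point holds as a small, optional improvement, not as an error. The stated PD model omits a baseline that is collected at both visits and already defined. Adding it costs at most about 1% in interval width if baseline is uninformative. It gains about 1% to 4% at r of 0.2 to 0.3 and about 13% at r = 0.5, with the lower part of that range more plausible. These sizes rest on assumed r, N = 66 and complete pairs. The primary analysis, the noninferiority conclusion and the sample size are unaffected.

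**What to change.** For raw log BGmax and raw log AUEC0-1.5, add the visit's pre-dose PG to the mixed model as two terms: its deviation from the patient's mean over both visits, and that mean. The split keeps differences between patients from distorting the within-patient slope. Prespecify the terms and the scale of the covariate (mg/dL or log) before data are seen. Report the planned unadjusted and baseline-adjusted versions alongside, and state in one line how the baseline adjustment in Section 10.3.4.1 is calculated.

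The cost is two parameters and a sentence or two of text, with no new data. Visits without a pre-dose value drop out of this model, and such a patient then adds nothing to the within-patient contrast. The unadjusted version covers that case. Under Section 10.3, a change that is not to a principal feature can be described and justified in the SAP without a protocol amendment.

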10.3.5. Pharmacokinetic/Pharmacodynamic Analyses

Exploratory analyses may be performed to evaluate exposure–response relationship if needed.

10.3.6. Data Review during the Study

Trial-level safety review will be conducted during the study by the study team.

10.3.7. Interim Analyses

No interim analyses are planned for this study. If an unplanned interim analysis is deemed necessary, the Lilly clinical pharmacologist, CRP/investigator or designee will consult with the appropriate medical director or designee to determine if it is necessary to amend the protocol.

A primary data lock will be conducted after last patient discharge from CRU. The aim of the primary data lock is to enable data analysis to assess the primary/secondary objectives, and may include assessment of exploratory objectives. The primary data lock will include all study data up to last patient discharge from CRU. There will be a final study data lock after all patients completed the safety follow-up visit.

11. References

Appendix 1. Abbreviations and Definitions

Term	Definition
AE	adverse event: Any untoward medical occurrence in a patient or clinical investigation subject administered a pharmaceutical product that does not necessarily have a causal relationship with this treatment. An AE can therefore be any unfavorable and unintended sign (including an abnormal laboratory finding), symptom or disease temporally associated with the use of a medicinal (investigational) product, whether or not related to the medicinal (investigational) product.
ALP	alkaline phosphatase
ALT	alanine aminotransferase
AUC	area under the concentration versus time curve
AUEC	area under the effect concentration-time curve
BGmax	maximal blood glucose
CI	confidence interval
C_{max}	maximum drug concentration
complaint	A complaint is any written, electronic, or oral communication that alleges deficiencies related to the identity, quality, purity, durability, reliability, safety or effectiveness, or performance of a drug or drug delivery system.
compliance	Adherence to all the study-related requirements, GCP requirements, and the applicable regulatory requirements.
confirmation	A process used to confirm that laboratory test results meet the quality requirements defined by the laboratory generating the data and that Lilly is confident that results are accurate. Confirmation will either occur immediately after initial testing or will require that samples be held to be retested at some defined time points, depending on the steps required to obtain confirmed results.
CRF	case report form
CRO	contract research organization
CRP	Clinical Research Physician: Individual responsible for the medical conduct of the study. Responsibilities of the CRP may be performed by a physician, clinical research scientist, global safety physician or other medical officer.
CRU	clinical research unit
DPC	dodecylphosphocholine
ECG	electrocardiogram

enroll	The act of assigning a patient to a treatment. Patients who are enrolled in the study are those who have been assigned to a treatment.
enter	Patients entered into a study are those who sign the informed consent form directly or through their legally acceptable representatives.
ERB	ethical review board
FSH	follicle-stimulating hormone
GCP	good clinical practice
HbA1c	hemoglobin A1c
HIV	human immunodeficiency virus
IB	Investigator's Brochure
ICF	informed consent form
ICH	International Council for Harmonization
LC-MS/MS	liquid chromatography with tandem mass spectrometry
IM	intra-muscular
IMG	intra-muscular glucagon
informed consent	A process by which a patient voluntarily confirms his or her willingness to participate in a particular study, after having been informed of all aspects of the study that are relevant to the patient's decision to participate. Informed consent is documented by means of a written, signed, and dated informed consent form.
investigational product	A pharmaceutical form of an active ingredient or placebo being tested or used as a reference in a clinical study, including products already on the market when used or assembled (formulated or packaged) in a way different from the authorized form, or marketed products used for an unauthorized indication, or marketed products used to gain further information about the authorized form.
investigator	A person responsible for the conduct of the clinical study at a study site. If a study is conducted by a team of individuals at a study site, the investigator is the responsible leader of the team and may be called the principal investigator.
IV	intravenous
legal representative	An individual or judicial or other body authorized under applicable law to consent, on behalf of a prospective patient, to the patient's participation in the clinical study.
NCA	noncompartmental methods of analysis

NG	nasal glucagon
non-investigational product	A product that is not being tested or used as a reference in the clinical study, but is provided to patients and used in accordance with the protocol, such as concomitant or rescue/escape medication for preventative, diagnostic, or therapeutic reasons, medication to ensure adequate medical care and/or products used to induce a physiological response.
open-label	A study in which there are no restrictions on knowledge of treatment allocation, therefore the investigator and the study participant are aware of the drug therapy received during the study.
PG	plasma glucose
PK/PD	pharmacokinetics/pharmacodynamics
randomize	The process of assigning patients to an experimental group on a random basis.
SAE	serious adverse event
SAP	statistical analysis plan
screen	The act of determining if an individual meets minimum requirements to become part of a pool of potential candidates for participation in a clinical study.
SUSAR	suspected unexpected serious adverse reaction
t_{1/2}	drug half-life
T1DM	type 1 diabetes mellitus
T2DM	type 2 diabetes mellitus
TBL	total bilirubin
TEAE	treatment-emergent adverse event: Any untoward medical occurrence that emerges during a defined treatment period, having been absent pretreatment, or worsens relative to the pretreatment state, and does not necessarily have to have a causal relationship with this treatment.
T_{max}	time to maximum concentration
ULN	upper limit of normal

Appendix 2. Clinical Laboratory Tests

Laboratory Tests

Hematology	Clinical Chemistry
Hematocrit	Sodium
Hemoglobin	Potassium
	Magnesium ^a
Erythrocyte count (RBC)	Chloride
Mean cell volume	Bicarbonate
Mean cell hemoglobin	Glucose ^d
Mean cell hemoglobin concentration	Blood urea nitrogen (BUN)
Leukocytes (WBC)	Total bilirubin
Platelets	
Differential WBC % of:	Albumin
Neutrophils	Alkaline phosphatase (ALP)
Lymphocytes	Aspartate aminotransferase (AST)
Monocytes	Alanine aminotransferase (ALT)
Eosinophils	Creatinine
Basophils	Phosphorus
HbA1c	
Urinalysis ^b	Other
Specific gravity	Ethanol breath testing ^c
pH	Urine drug screen ^c
Leukocyte esterase	Hepatitis B surface antigen ^a
Protein	Hepatitis C antibody ^a
Glucose	HIV ^a
Ketones	Pregnancy test (a serum pregnancy test will be done at screening, and urine pregnancy tests will be done prior to inducing hypoglycemia at the CRU visits in Periods 1 and 2)
Bilirubin	FSH ^a for confirmation of postmenopausal status
Urobilinogen	Pharmacogenetics
Blood	
Nitrite	
Color	

Abbreviations: CRU = clinical research unit; FSH = follicle-stimulating hormone; HIV = human immunodeficiency virus; RBC = red blood cell; WBC = white blood cell.

- ^a Performed at screening only
- ^b Microscopic examination will be performed only if dipstick test is positive for leukocyte esterase, blood, nitrite, or protein.
- ^c Urine drug screen and ethanol level may be repeated prior to admission to the CRU and at other times indicated in the Schedule of Activities (Section 2).
- ^d Random at screening and follow-up visits and fasting procedure visits.

Appendix 3. Study Governance, Regulatory, and Ethical Considerations

Informed Consent

The investigator is responsible for

- ensuring that the patient understands the nature of the study, the potential risks and benefits of participating in the study, and that their participation is voluntary.
- ensuring that informed consent is given by each patient or legal representative. This includes obtaining the appropriate signatures and dates on the ICF prior to the performance of any protocol procedures and prior to the administration of investigational product.
- answering any questions the patient may have throughout the study and sharing in a timely manner any new information that may be relevant to the patient's willingness to continue his or her participation in the study.
- providing a copy of the ICF to the participant or the participant's legal representative(s) and retaining a copy on file.

Recruitment

Lilly or its designee is responsible for the central recruitment strategy for patients. Individual investigators may have additional local requirements or processes. Study-specific recruitment material should be approved by Lilly.

Ethical Review

The investigator or appropriate local representative must give assurance that the ERB was properly constituted and convened as required by International Council for Harmonization (ICH) guidelines and other applicable laws and regulations.

Documentation of ERB approval of the protocol and the ICF must be provided to Lilly before the study may begin at the investigative site(s). Lilly or its representatives must approve the ICF before it is used at the investigative site(s). All ICFs must be compliant with the ICH guideline on GCP.

The study site's ERB(s) should be provided with the following:

- the current IB and updates during the course of the study
- ICF
- relevant curricula vitae

Regulatory Considerations

This study will be conducted in accordance with the protocol and with

- 1) consensus ethics principles derived from international ethics guidelines, including the Declaration of Helsinki and Council for International Organizations of Medical Sciences International Ethical Guidelines
- 2) applicable ICH GCP Guidelines
- 3) applicable laws and regulations

Some of the obligations of the sponsor will be assigned to a third-party organization.

Protocol Signatures

The sponsor's responsible medical officer will approve the protocol, confirming that, to the best of his or her knowledge, the protocol accurately describes the planned design and conduct of the study.

After reading the protocol, each principal investigator will sign the protocol signature page and send a copy of the signed page to a Lilly representative.

Final Report Signature

The investigator or designee will sign the clinical study report for this study, indicating agreement with the analyses, results, and conclusions of the report.

The sponsor's responsible medical officer and statistician will sign/approve the final clinical study report for this study, confirming that, to the best of his or her knowledge, the report accurately describes the conduct and results of the study.

Data Quality Assurance

To ensure accurate, complete, and reliable data, Lilly or its representatives will do the following:

- provide instructional material to the study sites, as appropriate.
- provide training to instruct the investigators and study coordinators. This training will give instruction on the protocol, the completion of the CRFs, and study procedures.
- make periodic visits to the study site.
- be available for consultation and stay in contact with the study site personnel through mail, telephone, and/or fax.
- review and evaluate CRF data and/or use standard computer edits to detect errors in data collection.
- conduct a quality review of the database.

In addition, Lilly or its representatives will periodically check a sample of the patient data recorded against source documents at the study site. The study may be audited by Lilly and/or regulatory agencies at any time. Investigators will be given notice before an audit occurs.

The investigator will keep records of all original source data. This might include laboratory tests, medical records, and clinical notes. If requested, the investigator will provide the sponsor,

applicable regulatory agencies, and applicable ERBs with direct access to the original source documents.

Data Collection Tools/Source Data

An electronic data capture system will be used in this study. The site must define and retain all source records and must maintain a record of any data where source data are directly entered into the data capture system.

Data Protection

Data systems used for the study will have controls and requirements in accordance with local data protection law.

The purpose and use of patient personal information collected will be provided in a written document to the patient by the sponsor.

Study and Site Closure

Discontinuation of Study Sites

Study site participation may be discontinued if Lilly or its designee, the investigator or the ERB of the study site judges it necessary for medical, safety, regulatory, or other reasons consistent with applicable laws, regulations, and GCP.

Discontinuation of the Study

The study will be discontinued if Lilly or its designee judges it necessary for medical, safety, regulatory, or other reasons consistent with applicable laws, regulations, and GCP.

